#### DLT excludes:

- Hematological and non-hematological  $\leq$  Grade 2 unless considered non-acceptable.
- Other Grade 3 self-limited or medically controllable toxicities (e.g., fever without  $\geq$  Grade 3 neutropenia, lymphopenia, nausea, vomiting, diarrhea, fatigue). Note, such events are considered DLT if the abnormality leads to hospitalization or the abnormality persists for  $>72$  hours despite appropriate interventions (e.g., replacement therapy for electrolyte abnormalities, when indicated).
- Electrolyte disturbances that are managed to Grade 1 or less with supplemental therapy.

Any adverse event that is potentially related to PTX-35 and requires discontinuation of treatment should be considered a DLT. A DLT will be considered related to PTX-35 treatment unless there is a clear, well-documented relation to intercurrent illness or primary malignant disease. AEs that meet the above criteria but occur after the DLT evaluation period will not be defined as DLTs but will be reported as AEs/Serious Adverse Events (SAEs), as applicable, and will be reviewed across all cohorts during the study to help inform dose escalation decisions.

In case of suspicion of a DLT, the Investigator must inform the Medical Monitor/Sponsor immediately. The DLT will be confirmed by the Medical Monitor/Sponsor and a decision must be taken by the Sponsor regarding if an *ad hoc* SRC meeting is required.

Patients who discontinue therapy before completion of 2 cycles (DLT period) for other reasons than dose-limiting toxicity will be replaced. Patients who are tolerating PTX-35 will not have to discontinue study treatment prematurely due to the occurrence of DLTs in another patient in the same cohort, unless decided by the SRC.

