### 6.1.3 Dose-Limiting Toxicity

An event will be considered a DLT per NCI CTCAE version 5.0 criteria if it occurs within the DLT reporting period during Cycle 1 and Cycle 2 (i.e., 4 week evaluation period following the initial administration of PTX-35) and meets at least one of the criteria below:

- Hematological toxicities  $\geq$  Grade 3
- Non-hematological toxicities  $\geq$  Grade 3
- Cytokine release syndrome  $\geq$  Grade 3
- Infusion reaction  $\geq$  Grade 3
- Any  $\geq$  Grade 3 hepatic toxicity meeting Hy's Law criteria, or total bilirubin  $\geq 2.0 \times$  ULN to  $\leq 3.0 \times$  ULN for  $>7$  consecutive days,  $\geq$  CTCAE G3 total bilirubin, CTCAE G3 AST or ALT for  $>7$  consecutive days, or CTCAE G4 AST or ALT
- Any other treatment-emergent toxicity that is considered clinically significant and/or unacceptable, and that does not respond to supportive care and results in a disruption of the treatment schedule of more than 14 days.

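### The DLT rule both counts and excludes a Grade 3 electrolyte event that is corrected to Grade 1 or less but lasted more than 72 hours or led to hospitalization

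*Combined protocol and SAP*

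**What the plan says.** Section 6.1.3 makes an event a DLT if it falls in the four-week window "and meets at least one of the criteria below". The list includes all non-hematological toxicity of Grade 3 or higher, with no duration. A separate hepatic criterion covers, among other things, Grade 3 AST or ALT lasting more than 7 "consecutive days, or CTCAE G4 AST or ALT".

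Three exclusions follow. The second removes "Other Grade 3 self-limited or medically controllable toxicities", subject to a note: "Note, such events are considered DLT if the abnormality leads to hospitalization or the abnormality persists for" more than 72 hours "despite appropriate interventions (e.g., replacement therapy for electrolyte abnormalities, when indicated"). The third removes "Electrolyte disturbances that are managed to Grade 1 or less with supplemental therapy".

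After the list, the section adds that a potentially related adverse event that "requires discontinuation of treatment should be considered a DLT". It also says that "The DLT will be confirmed by the Medical Monitor/Sponsor". The synopsis carries the same criteria and exclusions.

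**The concern.** The note and the third exclusion apply different tests to the same kind of event. The note asks how long the abnormality lasted and whether it led to hospitalization. The third exclusion asks only whether supplementation eventually brought it to Grade 1 or less. An event can meet both, and nothing says which then prevails.

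The number of DLTs is a primary endpoint (section 9.2.1), and the MTD, part of a secondary endpoint, is defined by it (sections 6.1.4 and 9.2.2). The count also drives the 3+3 steps in section 6.1.2. Without a rule, the decision on a disputed event is made after the event has been seen, in an open-label trial.

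**Working it through.** The documents state no figure that rests on this wording, so the check applies the lines to cases.

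**Electrolyte events of Grade 3, later corrected to Grade 1 or less, treatment not discontinued**

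| Duration | Led to hospitalization | Note to second exclusion | Third exclusion | Result |
|---|---|---|---|---|
| 48 h | No | Not a DLT | Excluded | Consistent: excluded |
| 120 h despite replacement | No | DLT | Excluded | Conflict |
| 48 h | Yes | DLT | Excluded | Conflict |

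If a potentially related event requires discontinuation, the later sentence in 6.1.3 makes it a DLT. The conflict is therefore confined to Grade 3 events in the DLT window that lasted more than 72 hours or led to hospitalization, were later corrected, and did not end treatment.

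**Effect of one disputed call under section 6.1.2**

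- Level of 3 with no other DLT: excluded gives 0/3, and escalation is permitted. Counted gives 0 + 1 = 1/3, and the level must expand to at least 6.
- Level of 6 with one other DLT: excluded gives 1/6, and the committee may recommend escalation. Counted gives 1 + 1 = 2/6, the MTD is exceeded and escalation ends.

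Levels without such an event are unaffected.

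**Frequency.** The documents give no rate. Section 2.6 reports one DLT of asymptomatic Grade 3 hyponatremia with a CD27 agonist, but not its duration, correction or any hospitalization. The monkey toxicology studies in section 2.4.2 report no drug-related clinical chemistry changes. No probability can be derived from these.

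**Grade 3 AST/ALT, not hospitalized, treatment not discontinued**

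- Literal reading of the criteria: a 5-day rise and an 8-day rise both meet the general Grade 3 criterion, and one criterion is enough. The 7-day limit separates nothing.
- If the second exclusion is also read as reaching hepatic tests, a self-limited rise that received no treatment might escape the 72-hour clause, because that clause refers to persistence despite intervention. If the hepatic criterion then survives the exclusion, it would count the rise after day 7, and the limit has some effect.

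The text does not choose between these readings.

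**The case against.** The strongest reply is that the specific line should prevail over the general one. On that view the third exclusion governs all electrolyte events, the word *Other* in the second exclusion points elsewhere, and the note's replacement example covers only disturbances that supplementation fails to correct. This reading is coherent, and the ambiguity does affect only a small subset. But it is not written down, and the note names electrolyte replacement explicitly. It would also exclude an event that put the patient in hospital, and it sets no deadline for correction.

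The safeguards are real. After 0/3, escalation is permitted rather than required. The Safety Review Committee sees all adverse events and can ask for more patients at a level (section 8.1.2.7.1). Related events above Grade 2 delay dosing (section 6.2). These limit harm to patients, but none says how to count the event. Confirmation by the Medical Monitor or Sponsor names a decision-maker and supplies no criterion.

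Three stronger inferences are tempting, and the documents do not support them:

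- *The 7-day AST/ALT limit never decides anything.* The second reading shown in the working gives it some effect. Where the limit is redundant, the rule is stricter, not looser. Section 6.3 also discontinues PTX-35 for immune-related Grade 3–4 toxicity, which already makes many such events DLTs.
- *Duration cannot be known, because chemistry in these cycles is scheduled only on Day 1, 14 days apart.* Section 8.1.2.1 requires adverse events to be followed to resolution or stabilization, and section 9.3 says the same of related events, so testing is not confined to scheduled draws. Neither sets a 72-hour test, so this answers the point only in part.
- *The escalation design is unsound, or a disputed call is likely.* The conflict is one of wording, and there is no rate to support a claim of frequency.

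**Conclusion.** The electrolyte conflict holds on the text of section 6.1.3 and the synopsis, with high confidence. It should be fixed because it leaves a primary-endpoint rule with two answers for the same event. Its size is one DLT per disputed event, which matters when the level stands at 0/3 or 1/6. How often that would happen is unknown. The conclusion assumes that the note covers electrolytes, which its own example supports, and that no precedence rule exists elsewhere; none was found in the documents.

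The AST/ALT overlap is a minor clarification. On a literal reading the 7-day limit has little or no effect, and the hepatic criterion was probably meant to govern, but the protocol does not say so.

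**What to change.** In section 6.1.3 and in the synopsis, end the third exclusion with *within 72 hours and without hospitalization*, so that it agrees with the note. If the sponsor instead intends correction to Grade 1 or less to prevail in every case, it should write that precedence explicitly and accept that a hospitalized event would not count. The first option is safer.

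In the same edit, state whether the general Grade 3 criterion or the hepatic criterion governs Grade 3 AST/ALT, and whether the second exclusion reaches hepatic tests.

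The cost is a wording change in two places. A few corrected electrolyte events will now count as DLTs, which may occasionally expand a level or end escalation where the other reading would not.

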#### **6.1.4 Maximum Tolerated Dose and Optimal Immunological Dose**

The MTD will be defined as the highest dose level at which  $\leq 1$  patient of at least 6 patients experienced a DLT during the first two treatment cycles. The OID will be defined as the dose level where increasing doses of PTX-35 do not result in increases in Treg activity (i.e., a plateau of Treg activity is observed). If the OID is reached prior to the MTD, further dose escalations may be discontinued by decision of the SRC.

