A post-treatment safety visit will be conducted approximately 30 days following the last dose of PTX-35. Response to treatment will be assessed according to RECIST 1.1 ([APPENDIX II](#)) with planned evaluation performed every 8 weeks ( $\pm$  1 week) from start of treatment (C1D1).

**Target number of patients:** Up to 22 - 34 total patients will be enrolled if all dose levels are evaluated.

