#### **Safety Review Committee:**

A Safety Review Committee (SRC) comprised of at least 3 members: one Investigator, a representative of Pelican Therapeutics, and the Medical Monitor. The SRC will evaluate the data obtained at each dose level and will recommend whether the dose should be escalated as per protocol, revised to a lower level or intermediate level, halted altogether or more patients are required at the same dose level to evaluate safety.

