No relevant toxicity of PTX-35 has been observed in a series of dedicated toxicology safety studies (mice and monkeys). Based on the experience with other antibodies, infusion reactions may occur. Manipulation of immune checkpoints may, theoretically, trigger immune-related adverse reactions and/or cytokine release syndrome but based on experience with other agonists of the TNFRSF, this risk appears limited with PTX-35.

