**Secondary:**

- To determine the optimal immunological dose (OID), or maximum tolerated dose (MTD) of PTX-35.
- To establish the pharmacokinetic profile of PTX-35.

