**Table 1: PTX-35 Dose Levels**

Dose level*	PTX-35 dose (mg/kg)	PTX-35 Concentration (mg/mL)	PTX-35 Dose (mL/kg)	Number of patients
1	0.01 mg/kg	1 mg/mL	0.01 mL/kg	3-6
2	0.03 mg/kg	1 mg/mL	0.03 mL/kg	3-6
3	0.10 mg/kg	1 mg/mL	0.10 mL/kg	3-6
4	0.30 mg/kg	5 mg/mL	0.06 mL/kg	3-6
5	1.0 mg/kg	5 mg/mL	0.20 mL/kg	3-6
6	3.0 mg/kg	5 mg/mL	0.60 mL/kg	3-6
7	10 mg/kg	5 mg/mL	2.0 mL/kg	3-6

*\*Dose levels 1 through 3 will be administered at a concentration of 1 mg/mL, and dose levels 4 through 7 will be administered at a concentration of 5 mg/mL.*

At each dose level, 3 patients will be enrolled, with a minimum waiting period of one week after treatment initiation of the first patient only. The remaining subjects in the dose level will be treated with no stagger. After all 3 patients in a dose level have received the second dose of PTX-35 and completed the DLT observation period, the Safety Review Committee (SRC) will review the safety data to make a dose escalation decision. If none of these 3 patients experiences a DLT, dose escalation may proceed. If 1 of these 3 patients experiences a DLT, the dose level will be expanded to at least 6 patients at the same dose level. If  $\leq 1$  out of 6 patients experiences a DLT, then the SRC may recommend dose escalation to the next dose level. If a DLT occurs in 2 or more patients in a particular dose level, the maximum tolerated dose (MTD) has been exceeded and dose escalation will cease. Up to 3 additional patients will be enrolled at the next lowest dose if only 3 patients were treated at that dose level, to confirm safety of that dose.

The conduct and completion of each subsequent dose cohort will follow in similar fashion until the MTD is established. Note that if the optimal immunological dose (OID), or observed plateau of Treg activity, is determined prior to MTD, further dose escalation may be discontinued by decision of the SRC.

Visits and study examinations will be performed per [Table 2: Schedule of Assessments](#). Safety will be assessed by frequency of treatment-emergent adverse events (TEAEs), evaluation of clinical laboratory parameters (hematology and biochemistry), weight, vital signs, electrocardiogram (ECG), performance status, and physical exam findings. NCI CTCAE version 5.0 will be used to grade all toxicities.

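### If no level has 2 or more DLTs and the top level has fewer than 6 patients, the MTD definition names a lower level that had a DLT, or no level

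*Combined protocol and SAP*

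**What the plan says.** Section 3.0 gives as a secondary objective: "To determine the optimal immunological dose (OID), or maximum tolerated dose (MTD) of PTX-35". The only text that declares an MTD is in Section 6.1.4, repeated in Section 9.2.2 and in the synopsis under Secondary Endpoints. It is the highest level at which no more than one "patient of at least 6 patients experienced a DLT during the first two treatment cycles".

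Escalation is governed by Section 6.1.2 (text after Table 1) and the same text in the synopsis:

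- "If none of these 3 patients experiences a DLT, dose escalation may proceed". A level can therefore be cleared with 3 patients.
- After 1 DLT in 3, the level is expanded to at least 6, and escalation is allowed if no more than 1 of 6 has a DLT.
- "If a DLT occurs in 2 or more patients in a particular dose level, the maximum tolerated dose (MTD) has been exceeded", and escalation ends.
- "Up to 3 additional patients will be enrolled at the next lowest dose if only 3 patients were treated at that dose level". This back-fill is described only for the level below one that was exceeded.

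The Safety Review Committee (SRC) may also find that "more patients are required at the same dose level to evaluate safety" (synopsis and Section 8.1.2.7.1). That power is discretionary and is not tied to the MTD definition or to the highest level. The SRC may stop escalation once the optimal immunological dose (OID) is found. No section says what to report if level 7 is cleared and no MTD can be declared.

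**The concern.** The definition needs 6 patients, while the escalation rule gives a well-tolerated level only 3. A level with no DLT in 3 patients therefore cannot be the MTD, while a lower level with 1 DLT in 6 can. If escalation reaches level 7 and level 7 ends at 0/3, the words of the definition point downward, to the highest level that happened to have a DLT and was expanded.

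This ending is plausible. Section 2.6 states that "No relevant toxicity of PTX-35 has been observed in a series of dedicated toxicology safety studies", in mice and monkeys. OID or MTD is the first secondary endpoint, and Section 9.8 bases the number of cohorts on identifying it. At stake is a reported MTD that lies below levels the trial itself cleared without a DLT, or an endpoint with no defined result.

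**Working it through.** **Step 1: the passages side by side.** Suppose level 3 (0.10 mg/kg in Table 1) ends at 1/6 and levels 4 to 7 each end at 0/3.

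- Escalation rule: level 3 clears at 1/6, and levels 4, 5, 6 and 7 clear at 0/3. No level has 2 DLTs, so no back-fill is called for.
- MTD definition: only level 3 has 6 patients with at most 1 DLT. It is the highest level that qualifies, although level 7 (10 mg/kg) was cleared with no DLT.

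If all seven levels end at 0/3, no level has 6 patients and none qualifies.

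**Step 2: where the passages agree.** If a level has 2 or more DLTs, the level below is brought to 6. If that level then has at most 1 DLT, it is the MTD under both texts. If level 7 itself has at most 1 DLT in at least 6 patients, it meets the definition directly. The conflict is confined to endings with no exceeded level and fewer than 6 patients at the highest level.

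**Step 3: how often.** The documents give no DLT rates and no operating characteristics, so there is no figure of the plan's own to reproduce. The rates below are assumptions. I also assume no SRC expansion beyond the written rule and no OID stop.

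For DLT rate p_k at level k:

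- a_k = (1 − p_k)³, cleared at 0/3
- e_k = 3p_k(1 − p_k)⁵, cleared at 1/6
- c_k = a_k + e_k, cleared

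Then, with products over levels:

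- lower level named, level 7 at 0/3: a_7 × (∏c_1..6 − ∏a_1..6)
- no level with 6 patients: ∏a_1..7
- level 7 at 1/6 (passages agree): e_7 × ∏c_1..6

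Worked for a flat 5%: a = 0.95³ = 0.8574; e = 3 × 0.05 × 0.95⁵ = 0.1161; c = 0.9734 (from unrounded a and e). So c⁶ = 0.8509 and a⁶ = 0.3972. Lower level named: 0.8574 × (0.8509 − 0.3972) = 0.389. No level with 6: a⁷ = 0.341. Level 7 at 1/6: 0.1161 × 0.8509 = 0.099. All seven clear: c⁷ = 0.828, which is the sum of the three apart from rounding.

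Rising curves, levels 1 to 7 in %: A = 1, 1, 2, 3, 4, 6, 8; B = 1, 2, 3, 5, 8, 13, 20; C = 1, 2, 4, 8, 15, 25, 35; D = 1, 2, 5, 10, 20, 35, 50.

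| Assumed rates | All 7 clear | Lower level named | No level with 6 | Level 7 at 1/6 |
|---|---|---|---|---|
| Flat 2% | 0.968 | 0.261 | 0.654 | 0.053 |
| Flat 5% | 0.828 | 0.389 | 0.341 | 0.099 |
| Flat 10% | 0.502 | 0.294 | 0.109 | 0.098 |
| A | 0.871 | 0.261 | 0.463 | 0.147 |
| B | 0.543 | 0.204 | 0.188 | 0.151 |
| C | 0.177 | 0.078 | 0.045 | 0.054 |
| D | 0.042 | 0.021 | 0.010 | 0.012 |

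Simulation with 400,000 trials per setting gives 0.261, 0.389 and 0.294 for the lower-level column at the flat rates, and 0.263, 0.204, 0.078 and 0.020 on A to D.

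**Step 4: sensitivity.** If the SRC fills level 7 to 6 patients in half of these trials, the lower-level column halves. If it always does so, the column is 0. OID stops lower it further, by an amount the documents do not allow one to estimate.

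**The case against.** **The sections should be read together.** Section 6.1.2 links the MTD to a level that was exceeded and then to confirmation at the level below, and it allows escalation to continue after 1/6. A sensible reader would not call level 3 the MTD when levels 4 to 7 were clean. That reading is fair, and it shows that 1/6 does not end escalation. It does not alter the only sentence that declares an MTD, which is repeated unchanged as the endpoint in Section 9.2.2.

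**There are other routes out.** The SRC may add patients, and an OID satisfies the endpoint without an MTD. Both stand. They are optional, and they are why the percentages are upper bounds with respect to filling level 7 or stopping for the OID. SRC additions at a lower level alone are not modelled.

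**The harm is limited.** This also stands. Analyses are descriptive by cohort and DLT counts are themselves a primary endpoint, so a reader would see the clean higher levels.

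Two stronger readings are tempting, and the documents support neither:

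- A reader might infer that an MTD always needs an exceeded level above it, so that level 7 at 1/6 should also be reported as MTD not reached. But that outcome meets Section 6.1.4 exactly, and withdrawing the label would redefine the endpoint.
- A reader might infer from the synopsis ("Up to 22 - 34 total patients will be enrolled if all dose levels are evaluated") that an ending without an MTD was planned. Seven levels of 3 need 7 × 3 = 21, and one level of 6 needs 6 × 3 + 6 = 24, so 22 falls between. But Sections 5.4.2 and 6.1.3 require replacement of patients who leave early for reasons other than toxicity. The figure may simply be 21 plus replacements.

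**Conclusion.** The point holds in one defined situation: no level with 2 or more DLTs, and fewer than 6 DLT-evaluable patients at the highest level given. There the written definition conflicts with the escalation rule, and gives either a wrong MTD label or none. The logic needs no assumed rates.

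The size does depend on assumptions. With no SRC expansion and no OID stop, a lower level is named in at most about 26%, 39% and 29% of trials at flat rates of 2%, 5% and 10%, and in 26%, 20%, 8% and 2% on curves A to D. With steep toxicity the problem is rare.

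The consequence is the label of a secondary endpoint. Escalation decisions, patient exposure and the primary endpoints are unaffected. It should be fixed because the rule as written yields the wrong answer and the remedy is wording alone.

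**What to change.** Reconcile Sections 6.1.2, 6.1.4 and 9.2.2 and the matching synopsis text by adding one sentence to 6.1.4, 9.2.2 and the synopsis:

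*If no dose level had 2 or more DLTs and the highest level administered has fewer than 6 DLT-evaluable patients, no lower level will be reported as the MTD; the result will be reported as MTD not reached, with the maximum administered dose and the DLT count and n at each level.*

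Keep the existing definition in every other case, including level 7 with at most 1 DLT in at least 6 patients.

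The cost is a few lines of text. It needs no added patients, samples or visits, and leaves the doses and escalation rule as they are.

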### **6.2 Dose Interruptions/Withholding**

Investigational Product may be withheld from a patient based on the Investigator's decision in the event of intercurrent illness, adverse event, administrative reasons, or other reasons. If the patient's condition subsequently improves, or the situation that resulted in withholding study drug rectifies itself, the Investigator may resume study treatment as soon as possible, unless the delay is more than 4 weeks.

Dosing should be delayed for any DLT-equivalent toxicity and possible CTCAE > Grade 2 adverse events considered related to study medication. At the Investigator's discretion, study treatment may recommence when the toxicity has resolved to Grade 2 or less. Immune related reactions or allergy should resolve to  $\leq$  Grade 1.

Treatment should be discontinued if a TEAE has not resolved (to acceptable grade) after  $\leq 4$  weeks.

[figure not shown]

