### **6.3 Dose Modification and Management of Immune-Related Adverse Events, Infusion Reactions, and Cytokine Release Syndrome**

One level dose reduction per the dose escalation scheme, for toxicity is allowed. If the toxicity is equivalent to a DLT (see Section 6.1.3) then continued treatment at a lower dose level needs approval by the sponsor and/or SRC.

If immune related adverse events occur, these should be managed according to the ASCO2018 guideline for immune checkpoint inhibitors, and therapy should be continued with close monitoring for Grade 1 toxicities, with the exception of some neurologic, hematologic, and cardiac toxicities. For Grade 2 toxicities, corticosteroids may be administered, and dose should be held until resolution of the AE. Grade 3-4 toxicities treatment with PTX-35 should be discontinued and treatment with high-dose corticosteroids initiated.

All patients should be observed for infusion-related reactions (e.g., back pain, fever and/or shaking chills, flushing and/or itching, alterations in heart rate and blood pressure, dyspnea or chest discomfort, skin rashes, or anaphylaxis). For Grade 1-2 reactions, the infusion should be temporarily interrupted and then resumed when symptoms are resolved. If symptoms have not resolved in 15 minutes treatment with acetaminophen and/or antihistamines may be administered per institutional standard at the discretion of the investigator. Premedication prior to subsequent doses is allowed and should be considered. Grade 3 or 4 infusion related reactions should be managed per institutional standards (e.g., IM epinephrine, followed by IV diphenhydramine and ranitidine, and IV glucocorticoid), and treatment with PTX-35 should be permanently discontinued.

Cytokine release syndrome (CRS) is associated with elevated circulating levels of several cytokines including interleukin (IL)-6 and interferon  $\gamma$ , and uncontrolled studies demonstrate that immunosuppression using tocilizumab, an anti-IL-6 receptor antibody, with or without corticosteroids, can reverse the syndrome. However, because early and aggressive immunosuppression could limit the efficacy of the immunotherapy, current approaches seek to limit administration of immunosuppressive therapy to patients at risk for life-threatening consequences of the syndrome. The treatment algorithm suggested by Lee et al outlined in Figure 4 should be used to manage such reactions.

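### After a DLT-equivalent toxicity, restarting PTX-35 at the same dose needs only the Investigator's discretion (6.2), while restarting at a lower dose needs sponsor and/or SRC approval (6.3)

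*Combined protocol and SAP*

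**What the plan says.** Section 6.2 sets the hold: "Dosing should be delayed for any DLT-equivalent toxicity and possible CTCAE" events above Grade 2 that are considered related. It then sets the restart: "At the Investigator's discretion, study treatment may recommence when the toxicity has resolved to Grade 2 or less". Immune-related reactions and allergy must first fall to Grade 1 or less. Treatment stops if an event has not reached an acceptable grade within 4 weeks. Section 6.2 names no restart dose, no approver and no upper limit on the original grade.

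Sections 4.5 and 6.1.2 give the default for patients who continue after two cycles: the dose and schedule stay unchanged, provided there is no unacceptable toxicity.

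Section 6.3 allows a reduction of one level for toxicity. If the toxicity is equivalent to a DLT, "then continued treatment at a lower dose level needs approval by the sponsor and/or SRC". It also contains two class-specific stops. For immune-related events it says "Grade 3-4 toxicities treatment with PTX-35 should be discontinued and treatment with high-dose corticosteroids initiated". For Grade 3 or 4 infusion reactions, "treatment with PTX-35 should be permanently discontinued". Cytokine release syndrome is referred to the algorithm in Figure 4, which is not reproduced in the text available for review.

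**The concern.** Set side by side, 6.2 and 6.3 put the approval step on the more cautious option. After a DLT-equivalent event, an Investigator who wants to go down one level must ask the sponsor or the SRC. An Investigator who resumes the dose that was being given when the event occurred need not.

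This is a first-in-human trial, and section 2.6 states that no human safety data exist. Dosing is every 2 weeks until progression, so a patient can be re-exposed soon after recovery. What is at stake is the safety of individual patients and uniform conduct across sites: two Investigators could follow the text faithfully after the same event and act under different levels of oversight.

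**Working it through.** The plan gives no figure to reproduce. The check compares the rules and then looks for any other section that supplies the missing approval.

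**Step 1: who controls a restart after a DLT-equivalent toxicity.**

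| Restart | Governing text | Approval required |
|---|---|---|
| Same dose | 6.2, with the default dose from 4.5 and 6.1.2 | None stated; Investigator's discretion |
| One level lower | 6.3 | Sponsor and/or SRC (either suffices) |
| After a Grade 3-4 immune-related event | 6.3 | Not applicable: discontinue |
| After a Grade 3-4 infusion reaction | 6.3 | Not applicable: discontinue permanently |
| After Grade 3 or higher cytokine release syndrome | Figure 4, not shown | Cannot be determined from the text |

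**Step 2: the exposure difference.** The doses in Table 1 (6.1.2) are 0.01, 0.03, 0.10, 0.30, 1.0, 3.0 and 10 mg/kg. The ratio of each dose to the one below it is:

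- level 2 to 1: 0.03/0.01 = 3.0
- level 3 to 2: 0.10/0.03 = 3.33
- level 4 to 3: 0.30/0.10 = 3.0
- level 5 to 4: 1.0/0.30 = 3.33
- level 6 to 5: 3.0/1.0 = 3.0
- level 7 to 6: 10/3.0 = 3.33

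A same-dose restart thus delivers 3.0 to 3.3 times the dose that would have needed approval. At level 1 Table 1 has no lower level, so the approval sentence in 6.3 has nothing to act on and 6.2 governs alone.

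**Step 3: does another section close the gap?**

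- Section 6.1.3: the Investigator reports a suspected DLT at once, and "The DLT will be confirmed by the Medical Monitor/Sponsor and a decision must be taken by the Sponsor" on whether the SRC meets ad hoc. Restart is not made to wait for either. The section is also tied to the first 4 weeks: "AEs that meet the above criteria but occur after the DLT evaluation period will not be defined as DLTs".
- Section 8.1.2.6: serious adverse events reach the sponsor within 24 hours throughout treatment. This covers later events if they are serious, but it is notification only.
- Section 5.4: therapy stops for unacceptable adverse events, or for toxicity that the Investigator judges to preclude more treatment. Neither item says that a DLT-equivalent event is unacceptable, and 6.2 plainly foresees restart after one.
- Section 5.5: dosing halts for a possibly related death, or for two or more possibly related Grade 4 events. A single Grade 4 event, or any number of Grade 3 events, does not trigger it.
- Section 8.1.2.7.1: the SRC reviews all adverse events and can meet ad hoc, but the recommendations listed there concern the dose level. Its approval role for an individual patient is in 6.3, for a lower dose.

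**Step 4: a concrete case.** Grade 4 AST or ALT is a DLT criterion in 6.1.3. If the event is not classed as immune-related, the 6.3 discontinuation rules do not reach it. Once it falls to Grade 2 within 4 weeks, 6.2 allows a restart at the same dose on the Investigator's discretion.

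**The case against.** The best reply is that the two sections have different jobs. Section 6.2 says when dosing may resume; 6.3 says at what dose, with whose approval, and when never. On that view a permissive sentence cannot override a specific instruction to discontinue, and all that is missing is a cross-reference.

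Much of this stands. A reader might infer that 6.2 allows a restart after a Grade 3-4 immune-related event or infusion reaction. The documents do not support that: the specific rules in 6.3 naturally govern those events. A reader might also infer that the Investigator acts with nobody else aware. That is not supported either. The sponsor hears of suspected DLTs and serious events promptly, it can convene the SRC, unacceptable adverse events end therapy, and unresolved events end it after 4 weeks.

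The reply fails on the remaining DLT-equivalent toxicities. Even if 6.3 is read as controlling, its approval sentence is confined to a lower dose, so a cross-reference alone would leave the same-dose restart without approval. It can also be said that Investigator-led rechallenge after recovery is a legitimate design choice. It is, but the sponsor has already decided that continuing at a reduced dose after such an event needs oversight, and that reasoning applies at least as strongly at full dose.

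**Conclusion.** The point holds, as a minor patient-safety matter. As written, the restart with 3.0 to 3.3 times the exposure has the weaker control. The finding is limited to DLT-equivalent toxicities outside the class-specific stops in 6.3, and it leaves open what Figure 4 says about cytokine release syndrome. It rests on reading the approval sentence in 6.3 as covering only what it names, a lower dose level.

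The documents give no expected rate of such events, so the number of patients affected cannot be stated. If no such toxicity occurs, the gap has no effect. The dose ratios describe exposure; they do not measure harm.

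A reader might infer that the DLT count, and so the escalation decision or the MTD, becomes uncertain. The documents do not support that. An event is counted under 6.1.3 whether or not the patient later restarts, and the sentence "Any adverse event that is potentially related to PTX-35 and requires discontinuation of treatment should be considered a DLT" is most naturally read as overriding the exclusion for controllable Grade 3 events.

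**What to change.** Amend 6.2 in two places:

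1. Require sponsor and/or SRC approval for any restart after a DLT-equivalent toxicity, at the same or a lower dose and at any time on study, with the restart dose recorded. Keep the Investigator's discretion for all other events.
2. State that 6.2 is subject to the discontinuation rules in 6.3.

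The cost is wording only: no new data, and no change to cohort size or the escalation rule. In conduct it adds one approval step per affected patient. The existing 4-week hold gives time to obtain it, but a slow decision could briefly delay a patient who would benefit from resuming.
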